8.12. Child Behavior Checklist for Ages 6-18 (CBCL)

The CBCL assesses behavioral and emotional status in children ages 6 through 18 years of age as reported by the parent/caregiver (Achenbach and Ruffle 2000; Achenbach 2005). The full CBCL has 2 parts, a Competence Scale (Parts I to VII) and a Syndrome Scale (behavioral items).

8.12.1. Competence Scale

The Competence Scale (Parts I to VII) assesses various activities, interpersonal relationships, and academic performance. Competence assessment will be performed at screening or day 1 visit and at the 53/ET visit.

The competence scale is divided into 3 subscales – see [Table 12](#).

Table 12: CBCL Competence Scale

Activities	Social	School
I.A. number of sports	III.A. number of organizations	VII.1. Mean performance
I.B. Mean part/skills	III.B. Mean Participation	VII.2. Special class
II.A. number of activities	V.1 number of friends	VII.3. Repeated grade
II.B. Mean part/skills	V.2 Frequency of contact	VII.4. School problems
IV.A. number of jobs	VI.A. Behavior with others	
IV.B. Mean job quality	VI.B. Behavior alone	

Total score and change from baseline for each subscale separately and a total score and change from baseline for all items will be summarized for each time point using descriptive statistics for continuous variables. Total scores are rounded to nearest 0.5.

Scores per item are calculated as follows in [Table 13](#):

Table 13: CBCL Competence Scale Scoring

Subscale	Item	Scoring
Activities	I.A. number of sports	count the number of sports.
	I.B. Mean part/skills	mean of up to 6 rates, 2 for each sport activity. Where 'below average' or 'Less than average'=0, 'Average'=1, 'above average' or 'More than average'=2.
	II.A. number of activities	count the number of activities.
	II.B. Mean part/skills	mean of up to 6 rates, 2 for each activity. Where 'below average' or 'Less than average'=0, 'Average'=1, 'above average' or 'More than average'=2.
	IV.A. number of jobs	count the number of jobs.
	IV.B. Mean job quality	mean of up to 3 rates, 1 for each job. Where: 'below average'=0, 'Average'=1, 'above average'=2.
Social	III.A. number of organizations	count the number of organizations.
	III.B. Mean Participation	mean of up to 3 rates, 1 for each organization. Where: 'Less active'=0, 'Average'=1, 'More active'=2.
	V.1 number of friends	'None'=0, '1'=1, '2 or 3'=2, '4 or more'=3.
	V.2 Frequency of contact	'Less than 1'=0, '1 or 2'=1, '3 or more'=2.
	VI.A. Behavior with others	mean of items a-c. Where: 'Worse'=0, 'Average'=1, 'Better'=2.
	VI.B. Behavior alone	rate for item d. Where: 'Worse'=0, 'Average'=1, 'Better'=2.
School	VII.1. Mean performance	Mean of up to 7 performance items. Where 'failing'=0, 'below average'=1, 'average'=2, 'above average'=3.
	VII.2. Special class	'Yes'=0, 'No'=1.
	VII.3. Repeated grade	'Yes'=0, 'No'=1.
	VII.4. School problems	'Yes'=0, 'No'=1.

Values of 'Do not know', 'Not applicable', or 'Has no brothers or sisters' will be ignored for mean calculations and logically skipped items will be imputed as 0 or none.

A subscale score is calculated as the sum of the item scores and the total score is calculated as the sum of the subscale scores. If one or more subscale scores are missing, the total score will not be calculated.

If 1 item from activities and social subscales has a missing value, the mean of the other items of that subscale is substituted for that item. If more than 1 item is missing from either of these scales or any item is missing from the school scale, the respective scale is not to be scored.

Results will be listed.

8.12.2. Syndrome Scale

The Syndrome Scale comprises 113 questions related to problem behaviors. Syndrome assessment will be performed at day 1, and at weeks 3, 7, 14, 27, 40, and 54/follow-up visits.

For each item, the parent/caregiver will circle '0' if the item is not true of their child, '1' if the item is somewhat or sometimes true, and '2' if the item is very true or often true.

The Syndrome scale is divided into 8 subscales – see [Table 14](#).

Table 14: CBCL Syndrome Scale

Anxious / Depressed		Withdrawn / Depressed	Somatic Complaints	Social Problems	Thought Problems	
14.Cries 30.FearsSchool 32.Perfect 35.Worthless 50.Fearful 71.SelfConsc 112.Worries	29.Fears 31.FearDoBad 33.Unloved 45.Nervous 52.Guilty 91.ThinksSuicide	5.EnjoysLittle 42.RatherBeAlone 65.Won'tTalk 69.Secretive 75.Shy 102.LacksEnergy 103.Sad 111.Withdrawn	47.Nightmares 49.Constipated 51.Dizzy 54.Tired 56a-g.Physical Problems without known medical cause ^a	11.Dependent 12.Lonely 25.NotGetAlong 27.Jealous 34.OutToGet 36.Accidents 38.Teased 48.NotLiked 62.Clumsy 64.PreferYoung 79.SpeechProb	9.MindOff 40.HearsThings 58.PicksSkin 60.SexPartsM 70.SeesThings 83.StoresUp 85.StrangeIdeas 100.SleepProb	18.HarmsSelf 46.Twitches 59.SexPartsP 66.RepeatsActs 76.SleepsLess 84.StrangeBehav 92.SleepWalk
Rule-Breaking Behavior		Attention Problems	Aggressive Behavior		Other Problems	
2.Alcohol 28.BreaksRules 43.LiesCheats 67.RunAway 73.SexProbs 82.StealsOther 96.ThinksSex 101.Truant 106.Vandalism	26.LacksGuilt 39.BadFriends 63.PreferOlder 72.SetsFires 81.StealsHome 90.Swears 99.Tobacco 105.UsesDrugs	1.ActsYoung 4.FailsToFinish 8.Concentrate 10.SitStill 13.Confused 17.Daydreams 41.Impulsive 61.PoorSchool 78.Inattentive 80.Stares	3.Argues 19.DemAtten 21.DestroyOther 23.DisobeySchl 57.Attacks 86.Stubborn 94.Teases 97.Threaten	16.Mean 20.DestroyOwn 22.DisobeyHome 37.Fights 68.Screams 87.MoodChang 89.Suspicious 95.Temper 104.Loud	6.BMOut 15.CruelAnimal 44.BiteNail 55.Overweight 74.ShowsOff 93.TalkMuch 107.WetsSelf 109.Whining 113.OtherProb ^b	7.Braggs 24.NoEatWell 53.Overeat 56h.OtherPhys 77.SleepsMore 98.ThumbSuck 108.WetsBed 110.WishOppSex

^aItem 56 stands for “Physical Problems without known medical cause: other” and may not be filled in by the responder.

^bSimilarly, item 113 that stands for “Any problems that were not listed above” may be missing, for the same reason.

Total score for each subscale separately, total score for all items, change from baseline for the total score for each subscale separately and change from baseline for total score for all items will be summarized for each time point using descriptive statistics for continuous variables.

Total score is calculated as the sum of items scores.

If more than 20 items have missing values, excluding items 56h and 113, which may be left blank by structure (see [Table 14](#) for details), then no scores will be provided. For calculating subscale scores, if one or more items, excluding items 56h and 113, are missing in a subscale, the subscale score will not be calculated.

Data will be listed.

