### 7.2.3. Child Behavior Checklist (for Ages 6 to 18)

The CBCL assesses behavioral and emotional status in children ages 6 through 18 years of age as reported by the caregiver ([Achenbach 2005](#), [Achenbach and Ruffle 2000](#)). The full CBCL has 2 parts, a Competence Scale (Parts I to VII) and a Syndrome Scale (behavioral items).

The Competence Scale (Parts I to VII) assesses various activities (eg, sports, hobbies, games, organizations, clubs, teams, groups, jobs, and chores), interpersonal relationships, and academic performance.

The Syndrome Scale comprises 118 questions related to problem behaviors. This study will use a recall period of “now or within the last week,” representing a modification from the original scale, which was “now or within the last 6 months”. For each item, the caregiver will circle 0 if the item is not true of their child, 1 if the item is somewhat or sometimes true, and 2 if the item is very true or often true.

The CBCL is part of the Achenbach System of Empirically Based Assessment that identifies syndromes that are behavioral clusters that indicate certain types of behavioral, social, or emotional problems ([Achenbach and Rescorla 2004](#)). The problem behaviors are scored on the following 8 empirically based syndromes: anxious/depressed, withdrawn/depressed, somatic complaints, social problems, thought problems, attention problems, rule-breaking behavior, and aggressive behavior.

The Competence and Syndrome Scales are displayed on profiles in relation to gender and age-specific percentiles and T scores based on national normative samples.

The full CBCL assessment (Competence Scale [Parts I to VII] and Syndrome Scale [behavioral items]) will be completed at the screening or day 1 visit, as applicable ([Table 4](#)) and at the week 53/ET visit ([Table 5](#)). The Syndrome Scale part of the CBCL [behavioral items] will be completed at day 1, as applicable ([Table 4](#)) and at weeks 3, 7, 14, 27, 40, and 54/follow-up visits ([Table 5](#)).

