
Statistical Analysis Plan

questionnaire will only be presented to patients aged ≥ 12 years. Children who turn 12 years old during the study will be administered C-SSRS (baseline/screening) as initial assessment during the study.

^p A full CBCL assessment (Competence Scale [Parts I to VII] and a Syndrome Scale [behavioral items]) will be performed at week 53/ET. The Syndrome Scale part of the CBCL assessment will be performed at weeks 3, 7, 14, 27, 40, 53/ET visit, and 54/follow-up visits.

^q For any dose adjustment, the investigator or designee should confirm that patients have the bottle that contains the appropriate tablet strength and quantity to complete the recommended daily regimen.

^r During the week 3 visit, the investigator (or designee) will make sure the patient receives the evening dose to complete the week 3 dosing for that day. Refer to the pharmacy manual for further details.

^s Study drug accountability will be assessed during in-clinic visits only. A check for compliance with TEV-50717 intake will be performed during each in-clinic visit and telephone contact after TEV-50717 has been dispensed.

^t Patients experiencing an adverse event leading to discontinuation of TEV-50717, or experiencing any other adverse event, should have a single blood sample collected for the measurement of TEV-50717, α -HTBZ and β HTBZ concentrations, if possible. This should be done (at the discretion of the investigator) as soon as possible after the onset of the ongoing adverse event and within 48 hours after the last dose intake in the case of TEV 50717 discontinuation. To permit the assessment of a potential relationship of the adverse event and plasma concentration, an estimate of the date and time of the last dose intake of study drug should be recorded along with the date and time of the sample collection. If the estimate of the dose intake cannot be established within a 2-hour window, then a blood sample should not be obtained.

^u Patients and/or caregivers will be instructed during the course of the study to notify the investigator if any new medication is prescribed, or if there is any change in current medication, including over-the-counter medications. Any prescribed medication should be reviewed with the investigator.

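### The SAP's CBCL Syndrome scoring key (Table 14) places every item number from 1 to 113 except 88, so one subscale, probably Aggressive Behavior, would be scored one item short if the gap is in the source document

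*SAP*

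**What the plan says.** SAP 8.12.2 states "The Syndrome Scale comprises 113 questions related to problem behaviors", each rated 0, 1 or 2. It adds "The Syndrome scale is divided into 8 subscales" and refers to Table 14 for the allocation. Table 14 has nine blocks: the eight subscales and a block of other problems.

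The Aggressive Behavior block has two columns. The first ends "57.Attacks 86.Stubborn 94.Teases 97.Threaten" and the second ends "68.Screams 87.MoodChang 89.Suspicious 95.Temper 104.Loud".

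On scoring, the SAP says "Total score is calculated as the sum of items scores". It reports each subscale and the all-item total, with change from baseline, at each time point. A subscale is not calculated if any of its items is missing, apart from 56h and 113, which may be blank by design.

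Protocol 7.2.3 gives a different count: "The Syndrome Scale comprises 118 questions related to problem behaviors".

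The SAP gives two lists of Syndrome visits:
- Section 8.12.2: "Syndrome assessment will be performed at day 1, and at weeks 3, 7, 14, 27, 40, and 54/follow-up visits".
- Section 2.2, Table 3 footnote p: "The Syndrome Scale part of the CBCL assessment will be performed at weeks 3, 7, 14, 27, 40, 53/ET visit, and 54/follow-up visits".

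**The concern.** Table 14 is the only scoring key that 8.12.2 points to, and the subscale scores are plain sums over it. An item that the key omits is dropped from its subscale at every visit for every patient. Change from baseline gives no protection: if a child's answer to that item worsens, that part of the change is lost. The item also falls outside the rule that withholds a subscale with a missing answer.

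CBCL is listed among the safety measures under the primary objective, and protocol 7.1.6 names changes in behavior as one of three kinds of event to be followed by scales. The SAP introduction says that the SAP prevails where the two documents differ, so the protocol's question count would not by itself repair the key.

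The two visit lists also differ at week 53, the visit at which drug is stopped, so they need to be made consistent.

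**Working it through.** **1. Item numbers.** The SAP's stated count is 113, and Table 14 can be compared with the set 1 to 113. It contains 112 distinct numbers, and the only one absent is 88. The only number that appears twice is 56, by design (56a-g under Somatic Complaints, 56h under other problems).

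**2. Responses per block**, counting 56a-g as 7:

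| Block | Responses |
|---|---|
| Anxious/Depressed | 13 |
| Withdrawn/Depressed | 8 |
| Somatic Complaints | 4 + 7 = 11 |
| Social Problems | 11 |
| Thought Problems | 15 |
| Rule-Breaking Behavior | 17 |
| Attention Problems | 10 |
| Aggressive Behavior | 8 + 9 = 17 |
| Other problems | 17 |
| Sum | 119 |

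Cross-check: item 56 supplies 8 responses under one number, so 112 + 7 = 119.

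**3. Comparison with the stated counts.** A complete key would hold 113 + 7 = 120 responses. Without 56h and 113, which the SAP lets stand blank, that is 120 - 2 = 118, the protocol's figure. Table 14 as it reads gives 119 - 2 = 117. So a complete key could explain both stated counts, 113 as numbered items and 118 as fixed responses. The protocol does not say that this is how it reached 118, so this reading is an assumption.

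**4. Where item 88 fits.** Five blocks are set in two columns. Reading each row by row:

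| Block | Entries in the two columns | Ascending row by row? |
|---|---|---|
| Anxious/Depressed | 7 and 6 | yes |
| Thought Problems | 8 and 7 | yes |
| Rule-Breaking Behavior | 9 and 8 | yes |
| Other problems | 9 and 8 | yes |
| Aggressive Behavior | 8 and 9 | no: ..., 86, 87, 94, 89, 97, 95, 104 |

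With 88 inserted between 86 and 94 in the first column, Aggressive Behavior has 9 and 9 entries and ends ..., 86, 87, 88, 89, 94, 95, 97, 104, which is ascending.

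**5. Size, if item 88 belongs to Aggressive Behavior.**
- Subscale maximum: 17 x 2 = 34 as listed, against 18 x 2 = 36.
- Share of the subscale's items lost: 1/18 = 5.6%.
- Loss per patient-visit: 0 to 2 points. A change score can be off by -2 to +2.
- Total, only if summed from the key: maximum 119 x 2 = 238 instead of 120 x 2 = 240.

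**6. Week 53.**

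| Source | Syndrome Scale at week 53/ET? |
|---|---|
| SAP 8.12.2 visit list | not listed |
| SAP Table 3 footnote p | yes |
| SAP Table 5 | yes, window days 326 to 374 |
| Protocol 7.2.3 | yes, as part of the full CBCL |
| Protocol Appendix C | yes, as part of the full CBCL |

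The 8.12.2 list has 6 post-baseline visits and footnote p has 7. The difference is week 53.

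**The case against.** The strongest objection is that the gap may not be in the SAP at all. Table 14 packs many short entries into multi-column cells, and converting a PDF to text can lose a line. Some footnote letters in SAP Tables 2 and 3 also look misread when set against the SAP's own footnotes and the matching protocol tables. The layout evidence cannot separate the two explanations, because a line dropped in conversion and a line omitted by the authors would look the same. This stands, and the point is therefore conditional on the source page.

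Second, the SAP defines the total over all items and states 113 questions. On that definition item 88 counts in the total wherever Table 14 puts it. This also stands: a reader might infer that the total always loses 0 to 2 points, but the text supports that only for a program that sums the total from the key.

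Third, no text assigns item 88 to Aggressive Behavior. The figures of 17 against 18 items and 34 against 36 points rest on layout.

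Fourth, a reader might take the 8.12.2 visit list to mean that the last on-drug Syndrome value is lost for all completers. The documents do not support that. Table 3 footnote p, the Table 5 window, protocol 7.2.3 and Appendix C all include the Syndrome Scale at week 53/ET, SAP 4.4 analyses scheduled visits at their scheduled week, and 8.12.2 itself summarises each time point. Protocol 7.2.3 also suggests how the wording arose: it uses a similar Syndrome-only list, but after saying that the full CBCL is given at week 53/ET.

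**Conclusion.** The point holds in conditional form. As Table 14 reads, item 88 has no place in the key. If the source page shows the same gap, a subscale programmed from the key is one item short at every visit and a missing answer to item 88 goes unnoticed. With item 88 in Aggressive Behavior, the size is 17 items instead of 18, a maximum of 34 instead of 36, and 0 to 2 points per patient-visit.

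This rests on three assumptions: the gap is in the SAP and not in the text conversion, item 88 belongs where the layout suggests, and the program follows Table 14.

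Severity is low to moderate. A reader might infer that a primary endpoint is mis-scored. CBCL is one of eight safety measures under the primary objective, no subscale is named as a primary endpoint, and the study is descriptive with no hypothesis test. The week 53 difference is an inconsistency of wording, with no loss of data.

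**What to change.** 1. Compare Table 14 with the source page of the SAP, and check the scoring program.
2. If the gap is confirmed, restore item 88 to the subscale given in the scoring manual.
3. State the number of items in each subscale and in the block of other problems, so that the key can be checked by its sum.
4. Reconcile the SAP's 113 questions with the protocol's 118, saying what each count includes.
5. Say whether the all-item total is summed from the key or over all items on the form.
6. Add week 53/ET to the Syndrome visit list in 8.12.2, to match Table 3 footnote p and Table 5.

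The cost is a text correction to the SAP before database lock and, if the program was built from the key, a matching change there. Study conduct and data collection do not change.

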8.13. Epworth Sleepiness Scale

The Epworth Sleepiness Scale (ESS) is a self-administered questionnaire composed of 8 questions that provide a measure of a patient's general level of daytime sleepiness ([Johns 1991](#)).

The ESS is administrated at screening and/or day 1 visit, and administered at weeks 3, 7, 14, 27, 40, 53/ET, and 54/follow-up visits.

The ESS is composed of 8 items. The responders are asked to rate their chances of falling asleep while engaged at 8 different activities, on a 4-point scale (0-3). Therefore, the total score can range from 0 to 24.

If at least 1 item has a missing value, then the entire questionnaire is not valid.

Total score of the 8 items and total scores change from baseline will be summarized by time point, using descriptive statistics. In the case of both caregiver and self-administered versions of the ESS are presented at the same visit, caregiver version will be used for patients who are 6 to 12 years old and self-administered version will be used for patients 13 years of age and older.

Total score is calculated as the sum of item scores.

Data will be listed.

8.14. Extrapyramidal Symptom Rating Scale

The Extrapyramidal Symptom Rating Scale (ESRS) consists of 2 subscales, ESRS I and ESRS II.

ESRS I and II are administrated at the baseline/day 1 visit and administered at weeks 3, 7, 14, 27, 40, 53/ET, and 54/follow-up visits.

8.14.1. ESRS I

The first subscale (ESRS I) is a 7 item subjective questionnaire to evaluate parkinsonism, akathisia, dystonia and dyskinesia. The ESRS I is scored on a 4-point scale (0=absent, 1=Mild, 2=Moderate, Severe=3) for each item.

Total score will be the sum of the 7 items. Missing item will be replaced by the average of the remaining responses within each item.

Total score and total scores change from baseline will be summarized by time point, using descriptive statistics.

Data will be listed.

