### 7.2.2. Extrapyramidal Symptom Rating Scale

The ESRS was designed to assess 4 types of drug-induced movement disorders: parkinsonism, akathisia, dystonia, and TD ([Chouinard and Margolese 2005](#)). In this study, parkinsonism and

akathisia will be evaluated with subscales I (subjective questionnaire) and II (evaluation for parkinsonism/akathisia). The ESRS is administered at the day 1 visit ([Table 4](#)) and administered at weeks 3, 7, 14, 27, 40, 53/ET, and 54/follow-up visits ([Table 5](#)).

Subscale I of the ESRS questionnaire rates subjective parkinsonism/akathisia at periods other than the day of examinations during the last 7 days. It is scored on a 4-point scale (0=Absent, 1=Mild, 2=Moderate, or 3=Severe). The evaluation takes into account the verbal report of the patient on the following: 1) the frequency and duration of the symptom during the day, 2) the number of days the symptom was present during the last week, and 3) the subjective evaluation of the intensity of the symptom by the patient.

Subscale II of the ESRS questionnaire for evaluation of parkinsonism and akathisia includes 17 items with scores ranging from 0 to 102 to assess the following: tremor (0 to 48), gait and posture (0 to 6), postural stability (0 to 6), rigidity (0 to 24), expressive automatic movements (0 to 6), bradykinesia (0 to 6), and akathisia (0 to 6).

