Assessment of drug-induced parkinsonism according to the ESR (subscale I and II), assessment of change in behavior according to the CBCL questionnaire, and assessment of sedation according to the ESS questionnaire will be summarized descriptively.

Safety assessments and time points are provided in [Table 5](#).

For continuous variables, descriptive statistics will be provided for actual values and changes from day 1 to each time point. For categorical variables, patient counts and percentages will be provided. Descriptive summaries of serious adverse events, patient withdrawals due to adverse events, and potentially clinically significant abnormal values (clinical laboratory or vital signs) based on predefined criteria will be provided as well.

If any patient dies during the study, a listing of deaths will be provided and all relevant information will be discussed in the patient narrative included in the CSR.

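### SAP 8.14.1 may add dystonia and dyskinesia items to the ESRS I total that the protocol uses for parkinsonism and akathisia; the item content needs reconciling and, if mixed, splitting

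*SAP*

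**What the plan says.** SAP 8.14.1 calls ESRS I a "7 item subjective questionnaire to evaluate parkinsonism, akathisia, dystonia and dyskinesia". On scoring it says "The ESRS I is scored on a 4-point scale", from 0 to 3 per item, and "Total score will be the sum of the 7 items". The planned output is this: "Total score and total scores change from baseline will be summarized by time point, using descriptive statistics". The data are also listed. No summary by symptom domain or by item is planned. For incomplete forms the rule is "Missing item will be replaced by the average of the remaining responses within each item".

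The protocol describes the subscale more narrowly. Section 7.2.2 notes that the full ESRS was built for four kinds of drug-induced movement disorder, then limits its use in this study to parkinsonism and akathisia, through subscales I and II. It adds: "Subscale I of the ESRS questionnaire rates subjective parkinsonism/akathisia at periods other than the day of examinations during the last 7 days". Section 9.6 names the purpose: "Assessment of drug-induced parkinsonism according to the ESR (subscale I and II)".

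ESRS subscales I and II are listed among the endpoints of the primary (safety) objective. The SAP Introduction says that the SAP prevails where the two documents differ. SAP section 11, on changes from the protocol's analyses, reads as not applicable.

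**The concern.** On the SAP's description, one unweighted sum holds two kinds of item. Some measure a toxicity that the protocol wants monitored. Others measure movements of the kind that define the disease: the protocol's Introduction characterises dyskinesia in cerebral palsy by dystonic and choreiform movements. Titration raises the dose in pursuit of less dyskinesia. If dyskinesia falls while parkinsonism emerges, the two changes enter the total with opposite signs.

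The study has a single arm and is descriptive, so no control group would reveal the offset, and change from baseline is the main thing a reader has. Protocol 7.1.6 defines no adverse events of special interest for expedited reporting and relies on standardised scores to follow drug-induced parkinsonism. A small mean change in the ESRS I total could therefore be taken as reassurance about parkinsonism that the number cannot give.

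**Working it through.** **Inputs.** SAP 8.14.1 gives 7 items, each scored 0 to 3, and an unweighted sum. The number of items on dystonia or dyskinesia, k, is given nowhere. It is treated as an assumption, from k = 1 to k = 6. There is no test, power figure or stated ESRS I range to reproduce.

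**Range.** 7 × 3 = 21, so the implied range is 0 to 21. As a check on reading the scale, the ESRS II parts in SAP 8.14.2 give 48 + 6 + 6 + 6 + 24 + 6 + 6 = 102 = 17 × 6, which matches the stated maximum.

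**Share of the range held by dystonia/dyskinesia items.** k × 3 / 21:
- k = 1: 3/21 = 14%
- k = 2: 6/21 = 29%
- k = 3: 9/21 = 43%

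**Offset in one patient.** Change in total = change in parkinsonism/akathisia items + change in dystonia/dyskinesia items. If each of the k items improves by d points, the rise in the other items that can be hidden is min(k × d, 3 × (7 − k)). With d = 1:

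| k | 1 | 2 | 3 | 4 | 5 | 6 |
|---|---|---|---|---|---|---|
| points hidden | 1 | 2 | 3 | 4 | 5 | 3 |

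At k = 6 the figure is capped by the one remaining item.

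Example with k = 2: two dystonia/dyskinesia items go from 2 to 1, and two parkinsonism/akathisia items go from 0 to 1. Total at baseline: 2 + 2 = 4. Total afterwards: 1 + 1 + 1 + 1 = 4. Reported change: 0. Change in the parkinsonism/akathisia items alone: +2.

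**Offset in a group mean (assumed values).** Suppose 20% of patients gain 3 parkinsonism/akathisia points and each dystonia/dyskinesia item falls by 0.5 on average.
- Parkinsonism/akathisia subtotal: 0.20 × 3 = +0.60
- SAP total, k = 1: 0.60 − 0.50 = +0.10
- SAP total, k = 2: 0.60 − 1.00 = −0.40
- SAP total, k = 3: 0.60 − 1.50 = −0.90

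These values show what the sum can do. They do not estimate what it will do here.

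**Missing items.** The wording of the replacement rule is unclear, since each ESRS I item has a single score. Read as the average of the other items, it mixes domains too. Take k = 2 with both dystonia/dyskinesia items at 0, four observed parkinsonism/akathisia items at 2, and the fifth missing. The filled value is (0 + 0 + 2 + 2 + 2 + 2)/6 = 1.33. Averaging within the domain gives 2.00.

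**The case against.** The best reply is that the premise may be wrong. Neither document lists the seven items. The mixed content rests on one descriptive clause in the SAP, and protocol 7.2.2 says "Subscale I of the ESRS questionnaire rates subjective parkinsonism/akathisia at periods other than the day of examinations". If the protocol is right, the SAP clause is a loose description and there is nothing to offset. This stands: the offset is conditional, and what the documents establish outright is a mismatch in how they describe the subscale.

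A reader might infer that the dystonia and dyskinesia items start high and will fall on treatment, so that the bias must run towards missing harm. The documents do not support that. They give no ESRS I baseline data, and protocol 1.3.1.1 says that efficacy in this disease is not yet established. Section 3.3 describes a mainly choreiform population, so a fall in any dystonia item cannot be assumed. The full scale was also designed to detect drug-induced dystonia and tardive dyskinesia, so a rise in such items could itself be a safety signal.

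A reader might also infer that the study would miss drug-induced parkinsonism. That goes too far. ESRS II, described as covering parkinsonism and akathisia only, has its own total and change by time point. Adverse events are summarised by severity and relatedness. Investigators review the scales for possible adverse events, and clinically significant neurological worsening is recorded as one. ESRS I data are listed, and no rule treats a zero mean change as evidence of no parkinsonism.

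These safeguards limit the consequence, but they do not make the ESRS I total interpretable. Subscale I covers the week outside the examination day, which ESRS II does not replace. Under Appendix M, remote visits may leave the rigidity and stability fields blank, and those belong to ESRS II. A listing lets someone find the problem later; it does not correct the summary table.

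**Conclusion.** The point holds conditionally. The two documents describe ESRS I differently, the SAP prevails, and its section 11 does not acknowledge the difference. If the SAP description is correct, the planned total combines the monitored toxicity with the treated condition, and the two can offset point for point for every k from 1 to 6. If the protocol description is correct, the offset disappears and only the SAP text needs correcting.

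The size is unknown because k is not stated; the worked figures rest on assumed values of k and of the changes. The direction is not established either: offset is possible, not shown to be likely. The effect is confined to the ESRS I summary and does not reach ESRS II or the adverse event tables. It still merits correction, because ESRS I is an endpoint of the primary objective in a study with no control arm.

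**What to change.** 1. State the content of the seven ESRS I items and reconcile SAP 8.14.1 with protocol 7.2.2. If the protocol description is right, correct the SAP clause; the splitting below is then not needed.
2. If dystonia or dyskinesia items are included, pre-specify which items belong to which domain. Summarise the parkinsonism/akathisia items separately from the dystonia/dyskinesia items, by time point and as change from baseline, with item-level shifts. Keep the seven-item sum as supplementary.
3. When a missing item is replaced, average only over items of the same domain, and reword the rule so that it says so.
4. Record the difference from the protocol in SAP section 11.

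The cost is SAP wording and one or two extra tables from data already collected. The one real downside is that the sub-score needs an item allocation that neither document now supplies; it should be fixed before database lock. No sample size or power figure changes.
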